#### 556 **6.4 Baseline information**

557 The following information will be recorded. For laboratory tests, the most recent value  
558 obtained for routine clinical practice is used, if available.

- 559 ● Clinical facility (e.g. name of treatment unit) enrolling patient.
- 560 ● Patient details (e.g. name, date of birth, sex).
- 561 ● Major comorbidities (e.g. malaria, HIV, tuberculosis, diabetes, malnutrition, previous  
562 *Filovirus* infection).
- 563 ● Date of *Filovirus* Disease symptom onset.
- 564 ● Date of admission to treatment facility.
- 565 ● Latest *Filovirus* test result (date, strain, Ct value).
- 566 ● Vital signs.
- 567 ● Focused symptom assessment (bleeding, confusion).
- 568 ● Biochemistry results (creatinine, ALT and/or AST).
- 569 ● Malaria test result.
- 570 ● Pregnancy test result (in women with childbearing potential) with estimated gestational  
571 age or trimester.
- 572 ● Contraindication to [each](#) of the study drugs.
- 573 ● Use of relevant concomitant medication (e.g. antivirals, corticosteroids, antimalarials).
- 574 ● Vaccination (including date) for *Filovirus*.

575

#### 576 **6.5 Randomised allocation of treatment**

577 All participants will receive usual standard of care guided WHO recommendations and can  
578 receive licensed therapies (where they exist). Randomisation will be undertaken using a  
579 web-based service.

##### 580 **6.5.1 Treatments**

581 Treatment and dosing information is provided in relevant annexes. Up to three arms will be  
582 active for a given virus.

- 583 ● Antiviral.
- 584 ● Monoclonal antibodies.
- 585 ● Host-directed therapy.

#### 586 **6.6 Administration of allocated treatment**

587 Treatments are provided open-label. Drugs will be prescribed by a clinician delegated by the  
588 principal investigator to do so, and administered by appropriately trained clinical staff.  
589 Treatments should be administered as soon as possible following randomisation (although

590 it is recognised that logistic issues may mean that initiation of some treatments may be  
 591 delayed). The patient's own doctors are free to reduce the infusion rate of the treatment or  
 592 stop study treatments if they feel it is in the best interests of the patient without the need for  
 593 the patient to withdraw from the study. Medications can be given to treat potential adverse  
 594 events (such as antihistamines, and corticosteroids (irrespective of allocation in trial)). [Virus-](#)  
 595 [specific annexes will provide](#) details regarding management of resumption of infusion for  
 596 specific treatments where required.

## 597 6.7 Schedule of assessments

598 Staff safety [takes precedence over study assessments](#). Where assessments are  
 599 undertaken for clinical need (e.g. RT-PCR), these are not duplicated as a study-specific  
 600 procedure.

601

## 602 Schedule of assessments

	B	D1	D2	D3	D4	D5	D6	D7	D8	D9	D10	D+	Death or discharge	D28	Pregnancy outcome
Baseline assessments															
Consent	X														
Name and demographics	X														
Clinical facility	X														
Clinical severity assessment	X														
Vital signs	X														
Malaria result	O §														
Pregnancy result a	X §												X b		X
Study assessments															
Survival													X	X	
RT-PCR Ct result	X §*	O	O	X	O	X	O	X	O	O	X	O	X	X	
Biochemistry (Cr, ALT and/or AST)	X			X		X		X			X				
Key medications	X												X	X	
Maternal and foetal outcomes	X												X		X

Safety assessments		R	R	R	R	R	R	R	R	R	R	R	R	R	R	R
Study treatment		R	R	R	R	R	R	R	R	R	R	R				

§ Most recent result prior to enrolment. X: study assessment (clinically collected samples will not be duplicated). O: result recorded when collected for clinical reasons but not collected as a study assessment. R: result collected when applicable. (a) in women of child-bearing age, (b) in women of child-bearing age discharged alive.

## 603 6.8 Monitoring of patients

604 Detailed guidance on procedures for monitoring patients during and after infusions will be  
 605 provided in trial standard operating procedures. In particular, patients should be monitored  
 606 during infusions sufficient for early recognition and treatment of anaphylaxis or other  
 607 infusion-related reactions, with emergency drugs (e.g. adrenaline, antihistamine) readily  
 608 available.

## 609 6.9 Collecting follow-up information

610 The following information will be ascertained at the time of death or discharge or at 28 days  
 611 after randomisation (whichever is sooner):

- 612 ● Vital status (alive / dead, with date and cause of death, if appropriate).
- 613 ● Hospitalisation status (inpatient / discharged, with date of discharge, if appropriate).
- 614 ● Results of *Filovirus* RT-PCR tests performed as part of routine clinical practice (date of  
 615 tests, positive / negative and Ct value).
- 616 ● Use of supportive treatment if available (e.g. blood products, non-invasive or invasive  
 617 mechanical ventilation, renal replacement therapy).
- 618 ● Use of any treatments included in this protocol (including drugs in the same class) or  
 619 other purported treatments for Filovirus Disease.
- 620 ● Participation in other randomised trials of interventions (vaccines or treatments) for  
 621 Filovirus Disease.
- 622 ● Result of repeat pregnancy test in women of child-bearing age.

623 Follow-up information is to be collected on all study participants who have not withdrawn  
 624 consent to follow up, irrespective of whether or not they complete the scheduled course of  
 625 allocated study treatment. If the trial team become aware of any deaths from direct or indirect  
 626 late effects of *Filovirus* infection after Day 28 these should be recorded.

### 627 6.9.1 Duration of follow-up

628 All randomised participants are to be followed up until death, discharge from hospital or 28  
 629 days after randomisation (whichever is sooner). Attempts may be made to contact patients  
 630 post-discharge to confirm vital status at day 28 but failure to do so will not be considered a  
 631 protocol deviation.

632 **6.9.1.1 Follow up of pregnant participants**

633 Additional data will be collected for women who are pregnant at the time of enrolment into  
634 the trial. Reasonable efforts will be made to follow-up pregnant women until the conclusion  
635 of their pregnancy to identify pregnancy outcomes, congenital anomalies and neonatal  
636 complications. This will be undertaken through structured telephone interviews with the  
637 mothers or their healthcare providers. Any maternal, neonatal or infant outcomes that  
638 constitute a potential SSAR will be reported to the Country Principal Investigator and  
639 managed in accordance with protocol. [Offspring of pregnant participants and neonates  
640 should be referred to national programmes for longitudinal follow up where these  
641 programmes exist.](#)

642 **6.10 Withdrawal of consent**

643 A decision by a participant that they no longer wish to continue receiving study treatment  
644 should not be considered to be a withdrawal of consent for follow-up. However, participants  
645 are free to withdraw consent for some or all aspects of the study at any time if they wish to  
646 do so. In accordance with regulatory guidance, de-identified data that have already been  
647 collected and incorporated in the study database will continue to be used (and any  
648 identifiable data will be destroyed). For participants who lack capacity, if their legal  
649 representative withdraws consent for treatment or methods of follow-up then these activities  
650 would cease. Withdrawal of consent will not affect supportive care provided at the clinical  
651 site, or participation or benefit from other programmes or research.

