#### 266 3.2.1 Pregnancy and breastfeeding

267 There is a high maternal mortality in pregnant women with Ebola Disease, and foetal  
268 survival is rare. There are only three known cases of Marburg Disease in pregnant women.  
269 All women died, and the only neonate delivered died shortly after birth. Therefore, pregnant  
270 women will be eligible for enrolment in the trial. Expert obstetric and teratology advice will  
271 be provided to the Trial Steering Committee prior to the inclusion of a new treatment in the  
272 protocol.

273 WHO recommends breastfeeding should be stopped in a lactating woman with Ebola  
274 Disease. There may be rare circumstances (e.g. a concordantly infected child younger  
275 than six months old without a safe feeding substitute) where a woman with a *Filovirus*  
276 infection continues to breastfeed. These decisions will be made independent of the trial. In  
277 the circumstance that a woman continues breastfeeding she would remain eligible for  
278 enrolment with any dose modifications [specified in virus specific annexes](#).

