### 308 3.4 Interventions

309 Details on the specific treatments included for each virus are described in virus specific  
 310 annexes.

311 **3.5 Study outcomes**

312 **3.5.1 Primary outcome**

- 313
  - All-cause mortality at 28 days following randomisation

314 **3.5.2 Secondary outcome**

- 315
  - Time (days) to *Filovirus* RNA <LLOQ (lower limit of quantitation) within 28 days

316 [Viral clearance, using results from study or routine clinical samples, is defined as

317 the first negative *Filovirus* RT-PCR test without a subsequent positive test result

318 or subsequent death. In the unlikely scenario that a patient is discharged home

319 without two successive negative RT-PCR tests, the date of the first negative test

320 or, if there is no negative test result, the date of medical discharge will be used.]

321 **3.5.3 Other outcomes**

- 322
  - Viral load (measured by cycle threshold) on blood samples taken at Day 3, 5, 7

323 and 10.

324 
  - Progression of organ dysfunction, measured on blood samples taken at Day 3, 5,

325 7, 10.

326 **3.5.4 Safety outcomes**

327 In addition to study outcomes (e.g. mortality), Adverse Events will be recorded if they fall

328 into one of the following groups:

329

- 330 a. Adverse Events of Special Interest (AESIs; e.g. infusion-related reactions).
- 331 b. Serious Adverse Events that are **not considered to be due to the underlying *Filovirus***
- 332 **infection.**
- 333 c. Serious (per standard regulatory definition) that are considered with reasonable
- 334 probability to be related to one of the study medications (i.e. Suspected Serious
- 335 Adverse Reactions, which includes Suspected Unexpected Serious Reactions
- 336 [SUSARs]).
- 337

338 Pregnancy and foetal outcomes will also be recorded.

339

340 Study outcomes will be assessed based on data recorded up to the time of death, hospital

341 discharge or 28 days after randomisation (whichever occurs first). Pregnant women will be

342 followed up to completion of pregnancy.

343

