## 652 7 DATA AND SAFETY MONITORING

653 In addition to study outcomes (e.g. mortality), Adverse Events will be recorded if they fall  
654 into one of the following groups:

- 655
- 656 1. Adverse Events of Special Interest (AESIs; e.g. infusion-related reactions).
  - 657 2. Serious Adverse Events that are not considered to be due to the underlying *Filovirus*  
658 infection.
  - 659 3. Serious (per standard regulatory definition) that are considered with reasonable  
660 probability to be related to one of the study medications (i.e. Suspected Serious  
661 Adverse Reactions, which includes Suspected Unexpected Serious Reactions  
662 [SUSARs]).
- 663

664 Pregnancy and foetal outcomes will also be recorded wherever possible to the end of the  
665 pregnancy.

666

667 Other adverse events will not be collected because of the severity of the underlying disease  
668 (including a high risk of mortality) and to avoid an excessive burden on staff working in a  
669 high-risk clinical environment. In this context, the occurrence of non-serious adverse events  
670 is of limited importance to regulatory and clinical decisions. All Adverse Events that meet  
671 one of the criteria above should be reported on the case report form.

672

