### 718 7.4 Pregnancy and foetal outcome.

719 Pregnant women who are enrolled in the trial will be followed until conclusion of the  
720 pregnancy. Pregnancy outcomes will be recorded in the case report form system.

721

722

---

† Serious Adverse Events are defined as those adverse events that result in death; are life-threatening; require in-patient hospitalisation or prolongation of existing hospitalisation; result in persistent or significant disability or incapacity; result in congenital anomaly or birth defect; or are important medical events in the opinion of the responsible investigator (that is, not life-threatening or resulting in hospitalisation, but may jeopardise the participant or require intervention to prevent one or other of the outcomes listed above).

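### Pregnancy follow-up is meant to identify neonatal complications but is scheduled to end with the pregnancy, so infant events after birth are not systematically captured

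*Protocol*

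**What the plan says.** Section 6.9.1.1 (Follow up of pregnant participants) states the duration and the purpose in one sentence: "Reasonable efforts will be made to follow-up pregnant women until the conclusion" "of their pregnancy to identify pregnancy outcomes, congenital anomalies and neonatal" complications. The information is to come from structured telephone calls to the mother or to those caring for her. No date is given for the call. The same section asks for neonatal or infant events to be reported when they may be SSARs, and for offspring to be referred to national follow-up programmes where there are any.

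Three other sections set the same end of follow-up:
- Section 3.5.4: pregnant women are "followed up to completion of pregnancy".
- Section 7: "Pregnancy and foetal outcomes will also be recorded wherever possible to the end of the" pregnancy.
- Section 7.4: "Pregnant women who are enrolled in the trial will be followed until conclusion of the" pregnancy.

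The schedule in section 6.7 has a final column for the pregnancy outcome, with a row for maternal and foetal outcomes, and nothing later.

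Section 3.2.1 justifies enrolling pregnant women by their poor prognosis. Of the three known Marburg cases in pregnancy it says: "All women died, and the only neonate delivered died shortly after birth".

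**The concern.** The purpose and the window in section 6.9.1.1 do not match. A congenital anomaly may be visible at delivery, but a neonatal complication or neonatal death comes after the stated end of follow-up. Without a stated postnatal time point, what is learned about a live-born infant depends on when someone happens to telephone.

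What is at stake is safety information on treatments given in pregnancy, some of them unlicensed (section 9.4). A death soon after birth, the kind of event that section 3.2.1 itself describes, could be found for one infant and not for another solely because of call timing or site practice. Because few live births are expected, each infant carries a large share of what the trial can say about safety in pregnancy.

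**Working it through.** No arithmetic in the plan is in question. The check is to set out every provision on pregnancy and infant follow-up and ask what it guarantees for a live-born infant.

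**Scheduled follow-up**

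| Section | Outcomes named | End of follow-up |
|---|---|---|
| 3.5.4 | Pregnancy and foetal | Completion of pregnancy |
| 6.7 (schedule) | Maternal and foetal | Pregnancy outcome column |
| 6.9.1.1 | Pregnancy, congenital anomalies, neonatal complications | Conclusion of pregnancy |
| 7 | Pregnancy and foetal | End of pregnancy, where possible |
| 7.4 | Pregnancy | Conclusion of pregnancy |

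Only section 6.9.1.1 names neonatal outcomes as a target, and no section adds time after delivery. Scheduled postnatal observation of an infant who is not itself a participant is therefore 0 days.

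**Other routes by which a postnatal event could reach the trial**

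1. *The telephone interview.* Its date is not fixed. Take the neonatal period as 28 days; this is an assumption, since the protocol gives no figure. A call d days after delivery then covers d/28 of it: 0/28 = 0% on the day of birth, 7/28 = 25% at one week, 28/28 = 100% at four weeks. The text is compatible with all of these.
2. *SSAR reporting.* This has no stated time limit and covers infants. It needs the trial team to hear of the event without a scheduled contact, and it needs a judgement that the drug is a reasonably probable cause. Section 7.3 directs attention to events that even a single case would tie strongly to the drug, and asks assessors to weigh filovirus disease as the alternative cause. A neonatal death after maternal infection may not pass that test. The route also yields no denominator.
3. *Enrolment of the infant.* Section 3.2 admits a newborn no more than seven days old whose mother has acute, laboratory-confirmed disease, without a positive test of its own. Section 6.9.1 then applies: "All randomised participants are to be followed up until death, discharge from hospital or 28" days, whichever is sooner. This does not cover an infant born after the mother has recovered, or an eligible infant who is not enrolled. Even for an enrolled infant, follow-up may stop at discharge.
4. *Referral to national programmes.* It depends on a programme existing, and the protocol states no return of data to the trial.

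Routes 1 to 3 can each capture some events. None ensures that the vital status and complications of every live-born infant are recorded to a common time.

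**The case against.** The strongest reply is that the end of pregnancy bounds follow-up of the woman, and that an interview asking about neonatal complications must by its nature take place after delivery. Call timing could be left to the standard operating procedures, and the virus appendices may add data collection. This stands in part: the authors plainly expected to hear about infants. But five sections place the end, or the last scheduled time point, at the pregnancy outcome. A reader of the protocol cannot tell whether infant status is to be known at one hour or at four weeks.

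Three stronger readings are tempting, and the documents do not support them.

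- *The record closes at birth with a live birth entered as a success.* The protocol does not say this. The interview date is unspecified rather than fixed at delivery, and no case report form is shown.
- *The Marburg neonate of section 3.2.1 would certainly be missed.* An infant of an acutely ill mother is the type that the newborn eligibility criterion targets, and if enrolled its death would count in the primary outcome. Enrolment is not automatic, so the case illustrates the kind of event at risk and is not a proven loss.
- *Between-arm comparisons of infant outcome would be biased.* The protocol plans no such comparison; pregnancy outcomes are recorded as safety information.

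Limited data collection is also a deliberate choice in this trial. That argues for keeping the addition small. It does not justify a window that stops short of its own stated target.

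**Conclusion.** The point holds as an internal mismatch in the protocol: the scheduled window ends before the neonatal complications that it is meant to identify. Infant deaths and complications after birth are outside scheduled follow-up and reach the trial only by chance of interview timing, by SSAR reporting, or through the infant's own enrolment.

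The effect is limited. Section 3.2.1 calls foetal survival rare, so few infants are involved, and the primary analysis of 28-day mortality does not change. The number of infants cannot be estimated from the protocol. The conclusion rests on the core protocol alone; a virus appendix or operating procedure that fixes an infant contact would reduce the gap, but the core text would still need to agree with it. The change is worth making because it is cheap and improves safety ascertainment, not because the main result is at risk.

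**What to change.** Reconcile sections 3.5.4, 6.7, 6.9.1.1, 7 and 7.4:

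- State one infant data-collection time point after a live birth. The end of a 28-day neonatal period, counted from delivery, is a reasonable example; that figure is a suggestion and does not come from the protocol.
- Hold the structured telephone interview already planned at or after that time point for live births, and add the time point to the schedule.
- Record infant vital status with date, neonatal complications, and congenital anomalies apparent by then.

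This concerns data collection only and alters no treatment or care. The cost is protocol and case report form wording, a later final record for a few pregnancies, and perhaps a few more mothers who cannot be reached. Deleting neonatal complications from the stated purpose would also make the text consistent, but it would give up the information.

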## 652 7 DATA AND SAFETY MONITORING

653 In addition to study outcomes (e.g. mortality), Adverse Events will be recorded if they fall  
654 into one of the following groups:

- 655
- 656 1. Adverse Events of Special Interest (AESIs; e.g. infusion-related reactions).
  - 657 2. Serious Adverse Events that are not considered to be due to the underlying *Filovirus*  
658 infection.
  - 659 3. Serious (per standard regulatory definition) that are considered with reasonable  
660 probability to be related to one of the study medications (i.e. Suspected Serious  
661 Adverse Reactions, which includes Suspected Unexpected Serious Reactions  
662 [SUSARs]).
- 663

664 Pregnancy and foetal outcomes will also be recorded wherever possible to the end of the  
665 pregnancy.

666

667 Other adverse events will not be collected because of the severity of the underlying disease  
668 (including a high risk of mortality) and to avoid an excessive burden on staff working in a  
669 high-risk clinical environment. In this context, the occurrence of non-serious adverse events  
670 is of limited importance to regulatory and clinical decisions. All Adverse Events that meet  
671 one of the criteria above should be reported on the case report form.

672

### 673 7.1 Adverse Events of Special Interest

674 AESIs will be reported on the case report form whether serious or not. They will include  
675 Infusion-Related Reactions (IRRs). An IRR is defined as an adverse reaction to an infusion  
676 of a study drug that occurs during or within one hour after completion of an infusion. These  
677 will be classified according to severity:

- 678
- 679 • Mild: no specific treatment required.
  - 680 • Moderate: treatment with antihistamines or steroids required.
  - 681 • Severe: treatment with adrenaline required, including anaphylaxis.

682 Further AESIs will be specified as necessary in the disease-specific annexes.

### 682 7.2 Serious Adverse Events that are not considered to be due to the underlying 683 *Filovirus* infection

684 In critically ill patients, a very large proportion of patients will suffer an SAE that is unrelated  
685 to the drug being evaluated. Recording SAEs that are a part of the natural history of the  
686 disease or are captured through primary or secondary endpoints does not add to reliable  
687 evaluation of the safety and efficacy of a drug. In fact, recording such data is more likely to  
688 reduce the likelihood of a reliable assessment since it will distract from the accurate and  
689 complete collection of more important data. In this trial the SAE of death is recorded through  
690 the primary endpoint. New or worsening events that meet the definition of an SAE and are  
691 considered by the site investigator to be unlikely to be related to underlying filovirus disease  
692 will be reported on the case report form.

